7 PARTICIPANT SELECTION

7.1 Study Population

At each of the four participating sites, we will identify all patients referred through the Emergency Department NCCT requests. Expected number of eligible participants and rationale behind sample sizing are detailed in the 'STATISTICAL CONSIDERATIONS' section.

7.2 Participant inclusion criteria

- Individuals undergoing Head CT scan at the ED / A&E (Accident and Emergency Services).
- Age \geq 18 years.
- Non-contrast axial CT scan series with consistently spaced axial slices.
- Soft reconstruction kernel covering the complete Brain.
- Maximum slice thickness of 6mm.

7.3 Participant exclusion criteria

- There are no explicit exclusion criteria for qER as all scans in inclusion criteria will be processed by qER. Exclusion criteria are implicit within the inclusion criteria listed above.

8 STUDY PROCEDURES

8.1 Consent

The study intervention is randomised and applied at an institutional level, and therefore individual patient consent is not required. We will not seek individual patient consent.

Data will be captured by the direct care team and anonymised before transfer to central research team at GSTT. Approval for the release of anonymised patient data for research purposes is integral to the ethics application through IRAS.

Under UK GDPR a patient may object to their data being used under certain circumstances. Should a patient involved in this study object to their data being used, then this will be processed by the site's information governance team using local standard operating procedures. If the objection is upheld, then the patient's data will be removed from the study.

qER solution is deployed through individual site agreements with qER, which include a local data processing agreement. Data sharing between sites and GSTT is governed by individual site data sharing agreements.

GP practices in the trust will be notified of the change in pathway through communication with each practice within the trust (GP letter in the Appendix).

Posters will be displayed within each radiology and emergency department detailing the deployment of qER to support radiology reporting (NHS service user/patient poster). Leaflets providing additional detail of the tool will be available on request (supporting patient information leaflet).

A patient co-investigator has reviewed early drafts of this protocol and we are planning on working with PPI groups in London and Oxford to provide further feedback on patient experience.

8.2 Sampling

During the pre-implementation period, data will be gathered on the current clinical pathway. Each site will provide data on volume of images and time periods from referral to acquisition and reporting of NCCT heads. This data collected during pre-implementation period will serve as the baseline data for final study analysis.

8.3 Data Collection

Evaluation sites will periodically collect, clean, link, de-identify and supply data in an agreed format, beginning with baseline data from the pre-implementation phase until the end of the post-implementation phase. The frequency of data collection is subject to change though depending on the feasibility of sites.

A data dictionary will be supplied (example included in the Appendix) that will support fulfilling these requirements from:

Extraction of routinely collected hospital data:

- Referral Data: Age, Sex, date of referral for CT, date of appointment. Where possible ethnicity and deprivation will be captured.

- Radiology Data: Number of referrals, Datetime CT acquired, Datetime CT reported, presence or absence of discordance between qER and reporting radiologist, CT device manufacturer/ type, Usual Care Report
- Clinical Data: Clinical Diagnosis, treatment initiation, referral, including date of death if applicable.
- Follow-up Data: Length of stay ED, Length of stay Hospital, Specialty pathway.
- qER data outputs from qER interpretation
- Changes in treatment pathways after implementation
- Time to diagnosis

Data linkage for follow-up (death within 28 days of Head-NCCT acquisition date) against outcomes will be collected for 28 days.

8.4 National Data opt-out.

If patient has selected National Data opt-out, their data will be excluded from final analysis.

8.5 Follow up Procedures.

Data linkage for follow-up (death within 28 days of Head-NCCT acquisition date) against outcomes will be collected 28 days after the Head-NCCT acquisition date.

9 MEDICAL EQUIPMENT (DEVICES)

qER, a CE Class II approved medical software device, detects, and localizes the presence of six target abnormalities - intracranial haemorrhage, cranial fracture, midline shift, mass effect, atrophy and hypodensities suggestive of infarcts in non-contrast Head-CT scans⁷. It uses pre-trained artificial intelligence algorithms to detect the presence or absence of the target abnormalities in Head-NCCT scans. This device has not been modified for the purpose of this research and will be used within its intended use for this study. The device will be deployed in all the four participating sites for the purpose of this study.

A priority status is assigned if any one of the target abnormalities (intracranial haemorrhage, cranial fracture, midline shift or mass effect) is detected by the software, and the user will be able to view a single summary slice listing all the target abnormalities found by qER on the CT scan followed by all slices in scan with the overlay of above abnormalities localization. Alternately, if none of the target abnormalities are detected, the output will indicate that the software has analysed the image and identified no critical findings. qER reports are intended to support certified radiologists and/or licensed medical practitioners for clinical decision making. It is a support tool and, when used with original scans, can assist the clinician to improve efficiency, accuracy, and turnaround time in reading head CTs. It is not to be used to provide medical advice, determine treatment plan, or recommend a course of action to the patient.

This study has been awarded funding from NHSx AI Award (Award reference: AI_Award02354).

Funding for the study team to deploy and use qER for the study purpose, to perform its analysis of the data gathered from sites, and to produce a final report, is confirmed under the research contract between Qure.ai (manufacturer of qER) and Guys and St Thomas' NHS Foundation Trust.

10 END OF STUDY DEFINITION

The end of the study is defined as the end of the 13th month following the study start date. Final data analysis shall follow this.

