2 SUMMARY/SYNOPSIS

| | |
|---|---|
| Title | A mixed methods study to assess the clinical effectiveness and acceptability of qER artificial intelligence software to prioritise CT Head interpretation |
| Protocol Short Title/Acronym | Assess the Clinical Effectiveness in Prioritising CT Heads (ACCEPT) |
| IRAS Number | 313507 |
| REC Reference | TO BE COMPLETED BEFORE SUBMISSION |
| EDGE reference | 141791 |
| Study Duration | 14 months |
| Health condition(s) or problem(s) studied | Radiological Turn-around-time (TAT) of Head-NCCT scan reporting |
| Primary objective | To assess if qER (an artificial intelligence-based prioritisation software for non-contrast CT (NCCT) head scans) tool-based reporting and triage significantly reduces report turnaround time (TAT) of prioritised NCCT head scans for patients attending the emergency department. |
| Secondary objective (s) | 
 • To assess utility of qER to support emergency department pathways for patients requiring NCCT head and radiology reporting workflow. • To assess the safety of qER at identifying patients with critical findings on NCCT heads. • To evaluate the technical performance of qER. • To conduct a Health Economic, cost utility analysis of qER. |
| End of study definition | The end of the study is defined as the end of the 28 days follow-up of the last patient undergoing CT within study period. Final data analysis shall follow this. |
| Number of Participants | About 16,800 Head-NCCT scans from patients presenting to ED department during the study period. |
| Study Type | Observational |
| Human Tissue Samples (if applicable) | Not applicable |
| Data collected/storage (if applicable) | Data will be collected and stored only within the internal participating sites |

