6 STUDY DESIGN & FLOWCHART

6.1 Study Design

6.1.1 Summary

A multi-centre stepped wedged cluster randomised study (Figure 1) will be conducted in 4 NHS hospitals over a 13-month period. Hospitals will be identified and initiated into the qER solution with a 30-day implementation period. The order in which sites will receive the qER intervention will be determined by computer-based randomisation. The stepped wedge design allows delivery of the intervention at an organisational level with evaluation of outcome measures at a patient level. Structuring the implementation through a staged activation in a random order provides important methodological advantages for both qualitative and quantitative elements of the study. The design allows control of adoption bias and adjust for time-based changes in the background patient characteristics at a patient level.

[figure not shown]

Figure 1: illustration of site initiation within the stepped-wedge design. Each square block represents a duration of 1 month.

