13 DATA

13.1 Data to be collected:

Evaluation sites will periodically collect, clean, link, de-identify and supply data in an agreed format, beginning with baseline data from the pre-implementation phase until the end of the post-implementation phase. The frequency of data collection is subject to change though depending on the feasibility of sites.

A data dictionary will be supplied (example included in the Appendix) that will support fulfilling these requirements from:

Extraction of routinely collected hospital data:

- Referral Data: Age, Sex, date of referral for CT, date of appointment. Where possible ethnicity and deprivation will be captured.
- Radiology Data: Number of referrals, Datetime CT acquired, Datetime CT reported, presence or absence of discordance between qER and reporting radiologist, CT device manufacturer/ type, Usual Care Report
- Clinical Data: Clinical Diagnosis, treatment initiation, referral, including date of death if applicable.
- Follow-up Data: Length of stay ED, Length of stay Hospital, Specialty pathway.
- qER data outputs from qER interpretation
- Changes in treatment pathways after implementation
- Time to diagnosis

Data linkage for follow-up (death within 28 days of Head-NCCT acquisition date) against outcomes will be collected for 28 days.

Data dictionary is attached as a separate document (Appendix 5).

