15 STATISTICAL CONSIDERATIONS

15.1 Sample Size

The sample size available for analysis is determined by the number of hospitals taking part in the study and the number of patients coming through the Emergency Department requiring a NCCT during the study period.

The proposed study is a stepped-wedge trial, in which all participating sites will receive the intervention, in a random order, throughout the study period. With 4 participating sites, within a 12-month study period, study sites will receive the intervention in a staggered manner (Figure 1). During the study, each site will have received the intervention at a certain time-point. The specific time point for when the site is will be switched from current standard pathway group to intervention group will be allocated based on randomisation procedure.

Baseline data for all sites prior to the start of the study will be available from electronic records. Follow-up data will be available throughout the study period, including at least 3 months post-intervention at all sites. It is likely that changes in treatment pathways after implementation will take time to reach a steady state, and one of the objectives of any analysis will be to model the transition from the pre-intervention to post-intervention state.

This design has elements of a cluster-randomised trial, and of a before-and-after study. Within each site, there will be sufficient statistical power to detect a 20% change in average outcomes (TAT measure) achieved before and after the implementation of the intervention.

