The power estimations were conducted via a simulation approach. The range of conditions for sample size and intraclass correlation coefficient (ICC) were tested. The values of sample sizes tested ranged from 120 to 600 abnormal scans per site per year, while the range of ICC ranged from 0.05 to 0.30. Assuming type I statistical error at the $\alpha=0.05$ level and the total duration of the study 12 months the generalized linear mixed-effect regression model (GLMM) with expected distribution of the outcome variable Gamma the total sample size of 1,680 abnormal scans (35 abnormal per site/month; total yearly per site 420) ensures satisfactory level of statistical power exceeding 80% for detecting reduction in TAT by 20%. The models were estimated for abnormal cases. Assuming that abnormal cases are only ~10% of all CT scans performed at sites it can be expected that the total number of available scans in this study will be 16,800. Simulations were performed in R version v.4.1.0. If the study was conducted in a single hospital, this would not provide definitive evidence. However, if a similar impact is observed across four sites, especially if the time course of changes in multiple outcomes track the implementation of the intervention within each site, then the study will provide compelling evidence of the impact of the intervention. Given the expected amount of data that will be generated as part of the study, then it is expected that there will be good power to detect intervention effects within subgroups of patients, defined by age, sex, deprivation, and final diagnosis.

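### Section 10 and the synopsis define the end of study differently, and under section 10 the last scans may not complete their 28-day death follow-up

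*Protocol*

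**What the plan says.** The protocol defines the end of the study twice.

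- Section 10: "The end of the study is defined as the end of the 13th month following the study start date". It continues: "Final data analysis shall follow this".
- Section 2 (synopsis): "The end of the study is defined as the end of the 28 days follow-up of the last patient undergoing CT within study period". The synopsis gives a study duration of 14 months.

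The length of the study also varies. Section 6.1.1 says the stepped wedge "will be conducted in 4 NHS hospitals over a 13-month period". Section 15.1 describes the design as "With 4 participating sites, within a 12-month study period", and its power simulation assumes "the total duration of the study 12 months".

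Death within 28 days of the scan is a secondary outcome (section 6.3). Section 8.5 says that linkage for it "will be collected 28 days after the Head-NCCT acquisition date". Sections 8.3 and 13.1 have sites supplying data "beginning with baseline data from the pre-implementation phase until the end of the post-implementation phase", although both also say that death linkage is collected for 28 days.

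**The concern.** If scanning continues to the end of month 13, section 10 closes the study with no time left to follow the last patients for 28 days. The data-supply wording in sections 8.3 and 13.1 points the same way, because it stops at the end of the post-implementation phase.

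The shortfall would fall on one condition only. Section 15.1 promises at least 3 months post-intervention at every site, so all scans in the last 28 days are aided. The data dictionary (Appendix 5, section 5.4.3) records 28-day death as a mandatory yes/no field with no code for incomplete follow-up, so an early extract could enter such patients as alive. (That field also counts from discharge rather than from the scan, a separate discrepancy.)

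At stake are a secondary outcome and the pre/post comparison of costs and health benefits in section 6.5, for which death is a listed data item. The date also has a regulatory use: the end-of-study declaration in section 11.2 runs from it.

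**Working it through.** **1. The plan's own volumes.** Section 15.1 gives 35 abnormal scans per site per month, 4 sites, 12 months, and about 10% of scans abnormal.

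- 35 × 4 × 12 = 1,680 abnormal scans, as stated.
- 1,680 / 0.10 = 16,800 scans in all, as stated.
- 16,800 / 365.25 = 46.0 scans per day.

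The protocol states no figure for 28-day mortality, so there is none to reproduce.

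**2. Follow-up of the last scan** = end of study minus end of scanning, with a month of 30.44 days.

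| Scanning ends | Study end per section 10 | Study end per synopsis |
|---|---|---|
| Month 12 (section 15.1) | 30.4 days | 28 days |
| Month 13 (section 6.1.1) | 0 days | 28 days |

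Only one of the four combinations loses follow-up. It uses the scanning length that best fits the synopsis: 13 months + 28 days = 13.9 months, close to the stated 14, whereas 12 months + 28 days = 12.9 months.

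**3. Scans affected in that combination.** 46.0 × 28 = 1,288 scans, of which about 129 are abnormal. In site time, 4 × 28 / 30.44 = 3.68 site-months, all aided.

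**4. Size of a crude bias.** This step assumes that deaths after the cut are not captured and that those patients count as alive. Then

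relative understatement = (3.68 / aided site-months) × (share of 28-day deaths missed in these scans).

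Aided site-months are an assumption, because Figure 1 is not shown. The lowest value, 12, is the 3-month minimum of section 15.1 at each of 4 sites. With scans spread evenly over the window, two assumed timings of death give the share missed:

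- deaths even over 28 days: 0.50;
- early deaths (exponential, mean 7 days, truncated at 28): 1 − [1/(1 − e⁻⁴) − 7/28] = 0.231.

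| Aided site-months | Share of aided scans affected | Even deaths | Early deaths |
|---|---|---|---|
| 12 | 30.7% | 15.3% | 7.1% |
| 18 | 20.4% | 10.2% | 4.7% |
| 24 | 15.3% | 7.7% | 3.5% |
| 29 | 12.7% | 6.3% | 2.9% |

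The range is about 3% to 15%. At an assumed true risk of 10%, the observed aided risk would be between 8.5% and 9.7%. The 15% end needs every site to have only the 3-month minimum, which a staggered roll-out would normally exceed.

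**5. Does adjustment for time help?** Expected rates without noise were fitted for 4 sites and 13 months, with assumed switch schedules, no true effect, and 23% or 50% of late deaths missed.

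| Adjustment | Rate ratio, aided vs unaided (truth 1) |
|---|---|
| Site and categorical month | 1.000 |
| Site and linear month | 1.005 to 1.12 |
| Site only | 0.89 to 0.97 |

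A month in which every site is aided offers no aided-versus-unaided contrast, so its own coefficient takes up the loss. The downward bias appears only when time is ignored; with a linear trend the error goes the other way.

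**The case against.** A reader might infer that the plan, as written, biases aided mortality downward. The documents do not support that.

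- No section says that scanning stops on the day section 10 ends the study. On the 12-month period of section 15.1, section 10 leaves about 30 days, enough for 28 days from the last scan.
- Nothing ranks section 10 above the synopsis or section 8.5, which already ties death linkage to 28 days after each scan.
- An end-of-study date is not a data cut-off. Deaths come from electronic records by linkage, and no section says that later deaths are discarded or that incomplete follow-up counts as survival. Handling of incomplete follow-up may lie in an analysis plan that is not shown.

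It is also tempting to say that calendar-month adjustment cannot help because the last month has no unaided scans. The reverse is true when month is categorical. Section 15.2 lists calendar month among its covariates, though it describes the model for turnaround time and does not give its form for mortality.

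The same argument could be extended to length of stay. That is a follow-up and resource-use item, not an outcome listed in section 6.3, and a patient still admitted may have a missing value rather than a shortened one.

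These objections stand against any claim of realised bias. They do not remove the contradiction: with 13 months of scanning, section 8.5 cannot be met by the section 10 date for the last scans.

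**Conclusion.** The protocol contradicts itself on when the study ends, and the 12-, 13- and 14-month durations leave the reader unable to tell which date governs. That much is certain from the text.

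The consequence for mortality is conditional. It needs 13 months of scanning, section 10 as the data cut, and unobserved deaths entered as survival. All three together would affect crude pre/post comparisons, including any feeding the economic model, by the 3-15% shown above, on assumed aided time and death timing. A mortality model with categorical month would be largely protected. The primary turnaround-time analysis is not touched. This is a correction worth making, not a threat to the main result.

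**What to change.** 1. Replace the section 10 definition with the one in the synopsis.
2. State a single scanning end date and use it consistently in the synopsis and sections 6.1.1, 10 and 15.1.
3. Say in sections 8.3 and 13.1 that the final death extract is taken no earlier than 28 days after the last scan, so that data supply extends beyond the post-implementation phase for this item.

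With the synopsis definition the last scan has 28 days of follow-up whether scanning runs 12 or 13 months. The cost is a few sentences and a final extract about one month later, which the 14 months in the synopsis already allow.

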11 ASSESSMENT OF SAFETY

11.1 Definitions

| | |
|-------------------------------------|--|
| 
Adverse events (AE)
 | 
An adverse event is any untoward medical occurrence, unintended disease or injury, or untoward clinical signs (including abnormal laboratory findings) in subjects, users, or other persons, whether related to the investigational medical device or not.
 
Note 1 to entry: This definition includes events related to the investigational medical device or the comparator.
 
Note 2 to entry: This definition includes events related to the procedures involved.
 
Note 3 to entry: For users or other persons, this definition is restricted to events related to the use of investigational medical devices.
 |
| 
Serious Adverse Event
 | 
An adverse event that led to any of the following:
 
 a. death, b. serious deterioration in the health of the subject, users or other persons as defined by one or more of the following: 
 1. a life-threatening illness or injury, or 2. a permanent impairment of a body structure or a body function including chronic diseases, or 3. in-patient or prolonged hospitalisation, or 4. medical or surgical intervention to prevent life-threatening illness or injury or permanent impairment to a body structure or a body function, c. foetal distress, foetal death or a congenital abnormality or birth defect including physical or mental impairment. |

| | |
|--|--|
| | Note 1 to entry: Planned hospitalisation for a pre-existing condition, or a procedure required by the protocol, without serious deterioration in health, is not considered a serious adverse event. |
| Serious adverse device event (SADE) | A serious adverse device effect (SADE) is any adverse device effect that has resulted in any of the consequences characteristic of a serious adverse event. A SADE may be anticipated or unanticipated. |
| Unanticipated Serious Adverse Device Effect (USADE) | Unanticipated serious adverse device effect (USADE) is a serious adverse device effect which by its nature, incidence, severity or outcome has not been identified in the current version of the risk analysis report. |

Recording and Reporting of Adverse Events

AEs must be recorded, assessed, reported, analysed, and managed in accordance with the Research Governance Framework for Health and Community Care and the study protocol. All AEs must be assessed for seriousness. AEs for this study will be recorded within the patient notes but are not considered reportable.

Recording and Reporting of Serious Adverse Events

Where an SAE requires recording; full details including the nature of the event, start and stop dates, severity, causal relationship to the device and/or trial procedures, and the outcome of the event will be recorded in the patient's medical notes. These events will be monitored and followed up until satisfactory resolution and stabilisation.

Assessment of causality

I.e., does the event have a "reasonable causal relationship" with any trial specific procedures or the investigational device?

The assessment of causality must be carried out by the PI or other medically qualified local investigator.

Assessment of expectedness

If the SAE is considered related to any trial specific procedures or the investigational medical device an assessment should be made of the expectedness i.e., is the SAE a recognised adverse effect of the investigational medical device or a trial procedure.

Reporting to Sponsor

The following events defined as USADEs are considered reportable to the sponsor.

- Any Serious Adverse Event that is considered related to the trial specific procedures, or the medical device(s) that is considered unexpected by the Chief Investigator or their delegate.
- Any device related serious adverse event that led or may have led to one of the following outcomes:
 - The death of a patient
 - A serious deterioration in the health of a patient.

A serious deterioration in health may include (non-exhaustive):

- Life threatening illness

- Permanent impairment of a body function or permanent damage to a body structure
- A condition necessitating medical/surgical intervention to prevent a) or b)
- Foetal distress or death, or any congenital anomalies or birth defects.

SAEs meeting the above criteria must be reported to the Pharmacovigilance (PV) Office immediately (within 24 hours) using the SAE form for a non CTIMP. The SAE form should be completed and signed by appropriately delegated staff. The form should be e-mailed to the PV Office and a copy placed in the Study Site File.

If all the required information is not available at the time of initial reporting, the CI (or designee) must ensure that any missing information is forwarded to the PV Office as soon as this becomes available. The report should indicate that this information is follow-up information for a previously reported event.

